#### **4.4 Secondary Performance Endpoint**

Key Secondary Performance Endpoints include:

- Freedom from any documented AF, AFL, or AT lasting >30 seconds at the last follow-up visit regardless of Class I or III AADs.
- Freedom from any documented AF, AFL, or AT lasting >30 seconds at the last follow-up visit absent of Class I or III AADs.
- Acute procedural success defined as documentation of sinus rhythm at the end of the procedure.

#### **4.5 Descriptive Endpoint(s) or Additional Data**

If necessary, additional analyses and endpoints will be defined in a separate Statistical Analysis Plan (SAP) prior to database lock.

### **5 SUBJECT SELECTION AND WITHDRAWAL**

#### **5.1 Subject Population**

This clinical investigation will enroll patients who have undergone concomitant surgical AF ablation using the CRYOF device. Subjects must meet all eligibility criteria and provide written informed consent prior to collection of study data.

#### **5.2 Subject Screening and Informed Consent**

##### **5.2.1 Subject Screening**

Potential subjects presenting at the clinical sites will be fully informed about the clinical investigation, following the established Informed Consent process (described in [Section 5.2.2]).

Subjects must be screened for clinical investigation eligibility by a member of the site's clinical investigation team previously trained to the protocol, and if applicable will be entered into a site-specific screening log.

In case the subject does not meet all inclusion criteria or meets any of the exclusion criteria, the subject is considered a screening failure. The Principal Investigator or the delegated clinical

investigation personnel will record the reasons for screen failure (e.g. inability to consent, refusal to consent, did not meet inclusion/exclusion criteria, death or major morbidity (such as stroke) etc.) on a screening log within the EDC as required.

Subjects meeting general inclusion criteria and no exclusion criteria will be asked to sign an Informed Consent form if they wish to participate in the clinical investigation. These subjects will also be entered into the screening log.

Subject data will be collected following enrollment into the clinical investigation and will be based on random selection of treated subjects.

### **5.2.2 Informed Consent**

The Informed Consent Form (ICF) must have the approval of the IRB or favorable opinion of the EC. While some institutions may request modification of the ICF to satisfy specific institutional requirements, the use of a modified or unique ICF is permitted if it meets the requirement of 21 CFR Part 50 and ISO 14155:2020 and is approved by the Sponsor.

The Investigator or his/her authorized designee will conduct the Informed Consent process, as required by applicable regulations and the center's IRB/EC. This process will include a verbal discussion with the subject on all aspects of the clinical investigation that are relevant to the subject's decision to participate, such as details of clinical investigation procedures, anticipated benefits, and potential risks of clinical investigation participation. Subjects must be informed about their right to withdraw from the clinical investigation at any time and for any reason without sanction, penalty or loss of benefits to which the subject is otherwise entitled. Withdrawal from the clinical investigation will not jeopardize their future medical care or relationship with the investigator.

During the discussion, the Principal Investigator or his/her authorized designee will avoid any improper influence on the subject and will respect subject's legal rights. Financial incentives will not be given to the subject. Subjects may be compensated for time and travel directly related to the participation in the clinical investigation. The subject shall be provided with the Informed Consent form written in a language that is understandable to the subject and has been approved by the center's IRB/EC. The subject shall have adequate time to review, ask questions, and consider participation. The Principal Investigator or his/her authorized designee will make efforts to ensure that the subject understands the information provided. If the subject agrees to participate, the Informed Consent form must be signed and dated by the subject and thereafter by the person obtaining the consent prior to any clinical investigation-specific procedures. The signed original will be filed in the subject's hospital or research charts, and a copy will be provided to the subject.

Failure to obtain informed consent from a subject prior to clinical investigation enrollment should be reported to Sponsor within 5 working days and to the reviewing center's IRB/EC according to the IRB's/ EC's reporting requirements.

If, during the clinical investigation, new information becomes available that can significantly affect a subject's future health and medical care, the Principal Investigator or his/her authorized designee (if applicable) will provide this information to the subject. If relevant, the subject will be asked to confirm their continuing informed consent in writing.

The ICF will clearly stipulate that the duration of the study is approximately 1.5 years, and the implications of this commitment will be reviewed and discussed with the subjects prior to enrollment in the study.

### **5.2.2.1 Special Circumstances for Informed Consent**

For eligible subjects in the U.S., an authorization for use and disclosure of the subject's protected health information, in accordance with the Health Insurance Portability and Accountability Act (HIPAA), must be obtained from the subject or their legally acceptable representative.

For subjects outside of the U.S. (OUS), a separate GDPR consent may be required if not already included within the ICF.

In addition,

- Individuals under the age of 18 or age of legal consent are excluded from the study population.
- Pregnant or breastfeeding women are excluded from the study population.

Incapacitated individuals, defined as persons who are mentally ill, mentally handicapped, or individuals without legal authority, are excluded from the study population.

For individuals unable to read or write Informed consent will be obtained through a supervised oral process. An independent witness will be present throughout the Informed Consent process. The written Informed Consent form and any other information will be read aloud and explained to the prospective subject or his/her legally acceptable representative and either will sign and personally date the Informed Consent form. The witness will also sign and personally date the Informed Consent form attesting that the information was accurately explained, and that informed consent was freely given.

## **5.3 Eligibility Criteria**

### **5.3.1 General Eligibility Criteria**

Assessment for general eligibility criteria is based on medical records at the site and interview with a candidate subject. Subjects must meet ALL of the inclusion criteria to be considered for the clinical investigation. If ANY of the exclusion criteria are met, the subject is excluded from the clinical investigation and cannot be enrolled.

### **5.3.2 Inclusion Criteria**

#### **5.3.2.1 General Inclusion Criteria**

All subjects recruited for study participation must meet all of the following inclusion criteria to be enrolled in the study:

1. Subject is greater than or equal to 18 years of age.
2. Subject has documented history of atrial fibrillation.
3. Subjects who received surgical ablation for their atrial fibrillation using CRYOF and on whom at least the following lesions were performed: left and right pulmonary vein isolation, roof and floor lines, mitral annulus line, a connecting lesion from left atrial appendage to left pulmonary vein, coronary sinus lesion, and LAA exclusion, with a lesion duration of at least 2 minutes.
4. Stable subject that underwent non-emergent cardiac surgical procedure(s) on cardiopulmonary bypass including open-heart surgery for one or more of the

following: mitral valve repair or replacement, aortic valve repair or replacement, tricuspid valve repair or replacement, and coronary artery bypass procedures, or atrial septal defect (ASD) repair.

5. Left Ventricular Ejection Fraction  $\geq 30\%$  (determined by echocardiography or cardiac catheterization performed within 90 days of enrollment as documented in subject medical history).
6. Subject is willing and able to provide written informed consent.
7. Subject is willing and able to return for scheduled follow-up visits.

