Only 12% of patients have Lone AF, leaving the remaining 88% with some form of structural heart disease.iii This structural heart disease commonly includes hypertension, coronary artery and valvular heart disease. Left untreated, AF can lead to ventricular dysfunction, atrial dysfunction, left atrial enlargement thus perpetuating the structural remodeling that causes and worsens atrial fibrillation and heart failure.iv

The relationship between progressive structural remodeling and atrial fibrillation explains why 88% of AF patients are persistent or permanent leaving only 12% as paroxysmal.v Furthermore, 76% of AF patients either have enlarged atria with diameter greater than 4.5 cm or an increase in left ventricular thickness.vi Atrial enlargement, as well as structural remodeling, determines the

incidence of atrial fibrillation and whether AF patients observe complications throughout their lifetime.

Patients newly diagnosed with AF are medically managed with multiple courses of antiarrhythmic drugs (AAD), and anticoagulants to lessen the risk of thromboembolic accidents. Within 5 years, most patients will become refractory to AADs, and will require additional intervention. Often AADs will have the effect of “dumbing down” the heart’s natural pacemaker, necessitating the need for permanent rate control. Although the risk of thromboembolism is reduced in the presence of anticoagulation, it is still substantially higher than that observed in the general population. In addition, bleeding complications from anticoagulation regimens occur at a cumulative rate of 1% per year.

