## **2 CLINICAL INVESTIGATION OVERVIEW**

### **2.1 Clinical Investigation Objective**

The primary objective of this study is to evaluate the safety and performance of the CRYOF device. The performance of the device will be demonstrated by establishing that the device effectively eliminates persistent and long-standing persistent atrial fibrillation in a clinically significant proportion of treated patients.

Treated subjects will be assessed for primary safety through 30-days post-procedure. Primary performance will be assessed at least through the 12-months post-procedure visit.

The minimum follow-up window will be at 12-months, with a maximum follow-up window at 24-months.

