## 5.4 Subject Enrollment

Subjects will be provided the IRB/EC approved ICFs and will have the opportunity to read, understand, and have their questions answered prior to signing the ICFs. If the subject agrees to participate in the study and signs consent, the ICF process will be completed. The subject must sign and date the ICF prior to collection of study data. The person reviewing the ICF with the subject will also sign and date the ICFs. The subject will be given copies of the signed ICFs to keep.

Upon entering subject enrollment information into Clindex, each subject will be assigned a unique identification (ID) number sequentially in ascending order. All subjects who sign the ICFs will be documented in a Screening and Enrollment Log. For subjects who sign the ICF but are ineligible to participate, minimum baseline characteristics: age, gender, race, screening date and screen failure reason (s) will be captured in Clindex.

A subject is considered enrolled in the clinical investigation from the moment the subject provides written informed consent and has been confirmed to meet all inclusion criteria and none of the exclusion criteria.

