#### **6.2.2 Baseline (within 30 days of index ablation procedure)**

- Inclusion/Exclusion criteria
- Demographic information (Age, Sex, Race, Ethnicity)
- Review of Medical and Cardiac history, including AF history
- Documentation of AF classification (Persistent or Longstanding Persistent)
- Vital History (Height, Weight, BMI, Blood Pressure, Heart Rate)
- NYHA Classification
- Heart Rhythm Assessment using 12 Lead ECG, if done
- ECHO (TTE) within 90 days of the procedure, if done
- Medications history – Antiarrhythmic drugs (AADs), anticoagulants including previous AAD treatment failures. Medication information should include:
  - Name and indication
  - Dosage with units and frequency
  - Start and stop dates

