## **7.6 Expected Morbidity/Procedural Complications Reporting**

For purposes of this study, the following events occurring within 48 hours of study procedures are not considered reportable (not recorded on eCRF but recorded in source documents) as they are normally expected to occur in conjunction with surgical treatment for non-paroxysmal forms of atrial fibrillation procedures (Maze III) or are associated with customary, standard care of subjects undergoing cardiac surgery:

- Chest pain without associated ECG changes
- Post-operative/post-procedure pain
- Post-anesthesia emesis, nausea, or headache (within 24 hours of procedure)
- Electrolyte imbalance without clinical sequelae following procedure, even if requiring correction
- Pre - planned future surgical procedures
- Low grade temperature increase (101°F or 38.5°C)
- Dizziness: Imprecise term commonly used to describe various symptoms such as faintness, giddiness, imbalance, lightheadedness, unsteadiness or vertigo.
- Elevated white blood count, outside the standard laboratory normal value, without signs and symptoms of infection
- Post-operative hematocrit decreases from baseline measured in the OR, prior to the first incision, not associated with hemodynamic changes, remaining above 25% and requiring < 2 units PRBC's
- Minor, localized tenderness, swelling, induration, oozing, etc. at surgical site.
- Sinus bradycardia/tachycardia that does not require treatment or intervention
- Systolic or diastolic blood pressure changes that do not require treatment or intervention.
- Any blood transfusions during preplanned operative procedures and unrelated to an adverse event.
- Thrombocytopenia: does not become an AE until treatment is administered.

- Atelectasis - collapse of lung tissue affecting part or all of one lung; the alveoli are deflated. This is not considered to be an AE unless treatment other than chest PT is required or it prolongs hospitalization.
- Hyperglycemia - The use of insulin in the post-operative period does not constitute hyperglycemia if during the same hospitalization. An elevated blood sugar of less than 250 mg/dl during the first 48 hours post-operative does not constitute hyperglycemia.
- Pleural effusion is not an event unless treatment with thoracentesis or chest tube insertion is required
- Pericardial effusion without hemodynamic compromise or treatment
- Atrial Fibrillation /Atrial Flutter/Atrial Tachycardia with or without cardioversion.

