### **8.1 Analysis Populations**

#### Intention-to-Treat Population:

The Intention-to-Treat (ITT) population consists of the subjects on whom the CRYOF device was used. This is the primary population for performance and safety endpoints.

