#### **8.2.1 Primary Performance Endpoint Analysis**

The primary performance endpoint is defined as freedom from any documented AF, AFL, or AT lasting >30 seconds at the last follow-up visit in the absence of Class I or III AADs (with the exception of previously failed AADs at doses not exceeding those previously failed). The primary performance endpoint is further defined in section 4.2 of the protocol.

Subjects meeting the primary performance endpoint will be labeled as “responders”, and the proportion of responders will be compared to a performance goal (PG) of 55%.

An exact binomial test will be conducted at a one-sided  $\alpha = 0.025$  level of significance to test the following hypothesis that the proportion of performance successes is significantly higher than the PG:

$$H_0: p \leq 0.55$$

$$H_A: p > 0.55$$

where  $p$  is the responder rate at last follow-up visit occurring at least 12-months post-procedure. The ITT population will be the primary population for this analysis.

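### The objective concerns persistent and long-standing persistent AF, but eligibility admits any documented AF, so the 55% test is not confined to the population of the claim

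*Combined protocol and SAP*

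**What the plan says.** - **Objective** (synopsis and section 2.1): performance is to be shown by "establishing that the device effectively eliminates persistent and long-standing persistent atrial fibrillation in a clinically significant proportion of treated patients".
- **Eligibility** (synopsis and section 5.3.2.1, no. 2): "Subject has documented history of atrial fibrillation". No AF type is required. Of the 25 exclusions in section 5.3.3.1, the nearest is no. 7, which limits AF duration to 10 years; none mentions paroxysmal AF. Section 1.1.2 defines paroxysmal AF as a class of its own.
- **Enrolment** (section 5.4): a subject is enrolled on giving consent, once the subject "has been confirmed to meet all inclusion criteria and none of the exclusion criteria". Section 5.3.1 likewise makes the two lists decisive.
- **Baseline data** (section 6.2.2): "Documentation of AF classification (Persistent or Longstanding Persistent"). No paroxysmal category is listed.
- **Analysis** (sections 8.1 and 8.2.1): the ITT population "consists of the subjects on whom the CRYOF device was used". It is the primary population for the exact test, in which "the proportion of responders will be compared to a performance goal (PG) of 55" per cent.
- **Subgroups** (section 8.5): no subgroup analyses are planned. Summaries by sex, race and other subgroups as needed are allowed, but AF type is not named.

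**The concern.** A subject with paroxysmal AF who meets the other criteria is validly enrolled, belongs to the ITT population and counts in the 55% test. No later step takes that subject out. The per-protocol set removes only major deviations, and enrolling such a subject is not a deviation. The baseline item has nowhere to record the class, so these subjects might not be separable afterwards.

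A pass would still be read against the objective, which names persistent and long-standing persistent AF. The data are meant for regulatory submission (section 1.1.5), and section 8.10 calls the treatment beneficial if both null hypotheses are rejected. If paroxysmal subjects do better, the pooled rate can clear the goal while the rate in the named population is no higher than 55%.

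**Working it through.** **Inputs from the protocol** (sections 8.2.1 and 8.3): goal p0 = 0.55; expected rate p1 = 0.68; one-sided exact binomial test at 0.025; 140 evaluable subjects; attrition 6.5%; 150 enrolled; threshold 89/140.

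**Assumed inputs:** the paroxysmal share f and the paroxysmal success rate p_par. The only share in the documents is in section 1.1.1: "88% of AF patients are persistent or permanent leaving only 12% as paroxysmal". That is a general AF figure, not this trial's. The 20% and 30% shares and the 60% and 80% rates are illustrations. The 68% is the trial's overall planning rate, borrowed here as a possible paroxysmal rate.

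**Step 1: reproduce the design.** Find the smallest r with P(X ≥ r | 140, 0.55) ≤ 0.025.
- r = 88 gives 0.0365 and r = 89 gives 0.0247, so the threshold is 89/140 = 63.6%, as stated.
- Power = P(X ≥ 89 | 140, 0.68) = 0.887, which agrees with the stated figure of more than 88%.
- 140 / (1 − 0.065) = 149.7, so 150 enrolled, as stated.

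The plan's own arithmetic is correct.

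**Step 2: chance of passing when the objective is not met.** Set the non-paroxysmal rate at exactly 0.55. The pooled rate is p = 0.55(1 − f) + f·p_par, and the chance of passing is P(X ≥ 89 | 140, p).

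| f | p_par | pooled p | chance of passing |
|---|---|---|---|
| any | 0.55 | 0.5500 | 2.47% |
| 0.12 | 0.60 | 0.5560 | 3.4% |
| 0.12 | 0.68 | 0.5656 | 5.5% |
| 0.12 | 0.80 | 0.5800 | 10.5% |
| 0.20 | 0.60 | 0.5600 | 4.2% |
| 0.20 | 0.68 | 0.5760 | 8.9% |
| 0.20 | 0.80 | 0.6000 | 22.0% |

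Fixing the paroxysmal count at 17 or 28 of 140, instead of letting it vary, changes little. For p_par = 0.68 and 0.80 the results are 5.5% and 10.4% with 17, and 8.8% and 21.4% with 28.

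**Step 3: eligibility stays open and the test is confined to non-paroxysmal subjects.** Take 140(1 − f) evaluable subjects, recompute the exact threshold, and evaluate power at 0.68. To keep 140 evaluable non-paroxysmal subjects, enrolment must be 140 / ((1 − f) × 0.935), rounded up.

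| f | n in test | threshold | power at 68% | enrolment to keep 140 |
|---|---|---|---|---|
| 0 | 140 | 89 | 88.7% | 150 |
| 0.12 | 123 | 79 | 84.0% | 171 |
| 0.20 | 112 | 73 | 77.2% | 188 |
| 0.30 | 98 | 64 | 75.4% | 214 |

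**The case against.** The strongest reply is that the intent is plain. The baseline item lists only the two non-paroxysmal classes. Section 7.6 speaks of "surgical treatment for non-paroxysmal forms of atrial fibrillation procedures (Maze III"), and section 7.1.1 refers to subjects with long-standing persistent AF. On this reading inclusion 2 is an incomplete line, not a decision to mix populations. That may well be so, but none of these places is an eligibility rule, and sections 5.3.1 and 5.4 let only the two lists decide.

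The opposite reading also has some support. The first sentence of the objective is general, section 5.1 describes patients who had concomitant surgical AF ablation, and the indication covers cardiac arrhythmias. This is why widening the objective must remain an option.

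The size of the effect is fairly called illustrative. The results run from no inflation to 22.0%, and no document figure says where this trial lies.

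Sections 4.5 and 8 allow a separate SAP to add endpoints or subgroup analyses, so AF type could be reported there. That is optional and would not change the primary ITT test.

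One caveat stands in full. The synopsis derives the performance criteria from literature on concomitant AF ablation and names no AF type. Both the 55% goal and the 68% expectation therefore need confirming for whichever population is chosen.

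**Conclusion.** The concern holds. Objective, eligibility and primary analysis population do not match, and no other section closes the gap. This follows from the text and does not depend on any assumed rate.

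The size is unknown. The inflation in Step 2 depends on the assumed paroxysmal share and on paroxysmal subjects doing better. With equal rates there is none, though the test would still not isolate the population of the claim. The stated sample size, threshold and power are correct for the pooled hypothesis. The mismatch should be reconciled because it bears on the primary claim and is cheap to correct.

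**What to change.** **Main change.** In the synopsis and in section 5.3.2.1, reword inclusion 2 to require a documented history of persistent or long-standing persistent AF before the index ablation procedure, as classified in section 1.1.2. The design stays at 140 evaluable and 150 enrolled, with threshold 89 and power 88.7%, if 68% suits that group; confirm the 55% goal for it too. The cost is one line in two places, that confirmation, and somewhat more charts to screen.

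**If paroxysmal subjects are already enrolled.** Add a paroxysmal category to the baseline item in section 6.2.2. Before any outcome data are reviewed, specify that the 55% test is run in persistent and long-standing persistent subjects, with the rest reported descriptively, and restate power in section 8.3. The cost is the loss of power shown in Step 3. Restoring 140 evaluable subjects in the test would take enrolment above the 150 maximum at each share shown.

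**If all AF types are intended.** Widen the objective in the synopsis and section 2.1 and the class list in section 6.2.2, and justify 55% and 68% for the mixed population. The pooled test can then stand.

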	
MAE rate of up to 8.5%, the sample size provides 80% power to demonstrate primary safety success.
 
Published literature on the safety and effectiveness of the concomitant AF ablation during cardiac surgical procedure was used to derive the performance criteria for the trial.

Inclusion Criteria	
 
1. Subject is greater than or equal to 18 years of age.
 
2. Subject has documented history of atrial fibrillation.
 
3. Subjects who received surgical ablation for their atrial fibrillation using CRYOF and on whom at least the following lesions were performed: left and right pulmonary vein isolation, roof and floor lines, mitral annulus line, a connecting lesion from left atrial appendage to left pulmonary vein, coronary sinus lesion and LAA exclusion, with a lesion duration of at least 2 minutes.
 
4. Stable subject that underwent non-emergent cardiac surgical procedure(s) on cardiopulmonary bypass including open-heart surgery for one or more of the following: mitral valve repair or replacement, aortic valve repair or replacement, tricuspid valve repair or replacement, or coronary artery bypass procedures, or atrial septal defect (ASD) repair.
 
5. Left Ventricular Ejection Fraction <math>\geq 30\%</math> (determined by echocardiography or cardiac catheterization performed within 90 days of enrollment as documented in patient medical history).
 
6. Subject is willing and able to provide written informed consent.
 
7. Subject is willing and able to return for scheduled follow-up visits.
 

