#### **2.2.4 Device Handling**

Subjects enrolled in this study will already have been treated, therefore device accountability is not required.

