#### **3.1 Clinical Investigation Procedures and Follow-up Schedule**

Clinical investigation sites that have treated subjects with the CRYOF surgical ablation system will be approached to determine if they are resourced and willing to consent subjects treated within the past 24-months post procedure for rhythm assessment via 24-hr rhythm monitoring.

The goal of this study is to collect data for patients in which the CRYOF device was used to produce a set of lesions that are based upon the standard Cox-Maze III lesion set (hereinafter referred to as “the optimum lesion set”), consisting of the following lesions:

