### **6.2 Follow-up Assessments**

#### **6.2.1 12-Month Visit ( $\geq$ 12-months but $\leq$ 24-months post index ablation procedure)**

Subjects will be consented 12 to 24 months post procedure and will be provided with a 24-Hour rhythm monitoring device at that time. The post procedure follow-up assessment will include:

- NYHA Classification
- 24-Hr Rhythm Assessment
- Evaluation of AEs/SAEs
- Medications – class I and III AAD's and anticoagulants, including any adjustments
- Review cardioversion since last visit

Note: If a clinical site is capable of remote subject visits, a modified visit assessment may be conducted. Remote subject visits should include Telemedicine appointments with the Investigator, where feasible, to allow direct engagement with the study subject and to ensure complete data collection. Rhythm monitoring devices may be provided to the subject either during an in-clinic follow-up visit, or shipped to the subject for a remote follow-up visit as applicable.

If clinical site is NOT able to perform remote subject visits, an attempt will be made to schedule the study subject visit as close to the visit window as is possible.

Regardless of when the subject is consented, the following data will be collected by reviewing the subjects' medical records retrospectively. For retrospective visits that fall outside of the required windows, please refer to sections 6.2.9 (Unscheduled Visit) and 10.6 (Protocol Deviations).

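### Inclusion criterion 5 dates the LVEF to within 90 days of enrollment; with consent at 12 to 24 months, neither a pre-operative LVEF nor the only echo the study collects can qualify

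*Combined protocol and SAP*

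**What the plan says.** Criterion 5 appears twice with the same anchor. Section 5.3.2.1 asks for an LVEF of at least 30% by echocardiography or catheterization "performed within 90 days of enrollment as documented in subject medical history", and the Synopsis has "performed within 90 days of enrollment as documented in patient medical history".

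Other sections fix what enrollment means and when it falls:

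- Section 5.4: "A subject is considered enrolled in the clinical investigation from the moment the subject provides written informed consent", once eligibility has also been confirmed.
- Section 2.2.4: "Subjects enrolled in this study will already have been treated".
- Section 5.3.1: "Subjects must meet ALL of the inclusion criteria to be considered for the clinical investigation".
- Section 6.2.1: "Subjects will be consented 12 to 24 months post procedure".

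The imaging the study collects is tied to the procedure. Section 6.2.2 lists a transthoracic echo from within 90 days of the procedure, where one was done. Section 6.2.8 ticks the echo at Visit 1 only. Neither section 6.2.1 nor the Visit 5 column of section 6.2.8 lists an echo.

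Consent timing is not stated consistently. Section 3.1 speaks of sites "willing to consent subjects treated within the past 24-months post procedure", which sets an upper limit and no 12-month minimum; section 6.1 does the same. The table in section 6.2.8 ticks consent and eligibility at Visit 1, whose window is 30 days around the procedure.

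**The concern.** For a trial of treated patients, one would expect the ejection fraction criterion to describe the heart the surgeon operated on. As worded, it describes the heart about a year or more later. Two consequences follow if a site applies the text as written under section 6.2.1.

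First, subjects are selected on a value measured after the treatment under study, and on having had an echo or catheterization in the 90 days before consent for reasons unrelated to the protocol. This is a single-arm study in which one responder proportion is tested against a fixed 55% goal (section 8.2.1), so who enters the denominator matters.

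Second, sites may not apply the text as written. With up to 20 sites, one could accept a pre-operative value, another could look for a late one, and a third could record a screen failure. A single mandatory criterion would then define different populations. The relief for retrospective data in section 10.6 does not settle this. It covers visit windows, NYHA class, 12-lead ECG and medication reviews, and does not mention LVEF or eligibility.

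**Working it through.** The plan gives no figure of its own on this point, so the check is date arithmetic.

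**Inputs.** Day 0 is the index procedure. Twelve months is taken as day 365 and 24 months as day 730. C is the day of enrollment. The 90-day window is from criterion 5, the range of C from section 6.2.1, and the echo window from section 6.2.2.

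**Step 1, the window.** Eligibility must be confirmed for enrollment to occur (section 5.4), so the LVEF must be dated from C − 90 to C.

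**Step 2, consent at 12 to 24 months.**

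| | C = 365 | C = 730 |
|---|---|---|
| Window opens, C − 90 | day 275 | day 640 |
| Window closes, C | day 365 | day 730 |
| Shortfall of a pre-operative LVEF (day 0 at the latest), C − 90 − 0 | 275 days | 640 days |
| Shortfall of the collected echo if dated day +90, C − 90 − 90 | 185 days | 550 days |

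The last row reads the echo window as extending to 90 days after surgery. That is the most lenient reading, used as a bound; the plan does not say the echo is post-operative. If the echo is pre-operative, the row above it applies. The collected echo fails on both readings.

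**Step 3, month length.** With 30-day months, 12 months is day 360 and the window opens at 360 − 90 = day 270. With 30.5-day months, it is day 366 and the window opens at day 276. The conclusion does not change.

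**Step 4, how early consent would have to be.** A day-0 LVEF needs C − 90 ≤ 0, so C ≤ 90. At C = 91 the window opens on day 1 and every pre-operative value is out. An echo at day +90 needs C − 90 ≤ 90, so C ≤ 180. Both limits are well short of the 12 months in section 6.2.1.

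**Step 5, the consent passages side by side.** Sections 3.1 and 6.1 allow any time up to 24 months, which includes consent by day 90 but does not require it. The Visit 1 tick in section 6.2.8 sits before the Procedure visit. Because all subjects have been treated before they enroll, the tick cannot literally date consent to a pre-procedure visit. Section 6.2.1 is the only passage that gives both ends of a consent window.

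**The case against.** **Consent may be earlier than 12 months.** Sections 3.1 and 6.1 set no minimum, and section 6.2.1 itself goes on to say "Regardless of when the subject is consented". That phrase follows the 12-to-24-month sentence and can simply mean anywhere in that range. The objection shows a second inconsistency in the protocol; it does not remove the first, since a pre-operative LVEF works only with consent by about day 90.

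**The criterion can still be met.** This stands. Criterion 5 relies on the medical history, section 5.3.1 bases eligibility on site records, and section 11.3 requires source records adequate to verify entry criteria. A routine-care LVEF close to enrollment would do. A reader might infer that no subject can qualify, but the documents do not support that.

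**A current-status check may be intended.** Also possible. In section 5.3.3.1, exclusions 4, 6, 8 to 11, 19 and 20 are tied to the index procedure, but 14 and 16 to 18 are in the present tense, so enrollment wording could be deliberate. The protocol does not say so, and it collects no LVEF at that time.

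**The baseline window dates source data, not the eligibility check.** This stands. A reader might take the inclusion/exclusion entry at the baseline visit to mean that the check is made within 30 days of the procedure. Sections 6.1, 5.3.1 and 5.4 place the check at chart review and enrollment, and section 6.2.1 introduces the earlier visits as retrospective record review. The conflict therefore lies between the LVEF window, the consent timing and the collected echo.

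**Conclusion.** The point holds. With consent at 12 to 24 months, criterion 5 admits only an LVEF from about day 275 or later, excludes every pre-operative value by at least 275 days, and cannot be satisfied by the one echo the study collects. This rests on two assumptions: that section 6.2.1 governs consent timing, and that the LVEF must exist when eligibility is confirmed. If consent were by about day 90, a pre-operative value could qualify.

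A reader might go further and infer that the responder rate is biased in the device's favor. The documents do not support that: they do not say how many patients have late imaging, why they have it, or how late LVEF relates to rhythm outcome. Neither size nor direction can be derived. What is established is a mandatory criterion that does not fit the stated enrollment timing. Differing application across sites is a plausible consequence, not a demonstrated one.

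**What to change.** Reconcile criterion 5 in the Synopsis and section 5.3.2.1 with sections 6.2.1, 6.2.2 and 6.2.8, so that one LVEF anchor date applies.

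- **Anchor.** Dating the window to the index procedure would match the baseline echo window in section 6.2.2 and the wording of many exclusions in section 5.3.3.1. If a current-status check at enrollment is intended, say so and record that LVEF.
- **Data.** In either case, add a field for the LVEF value, date and method (echo or catheterization), taken from the chart. Changing the anchor alone would not make the criterion checkable from data already collected: the echo is collected only where done, and catheterization, which criterion 5 accepts, is not listed.
- **Consent.** State the consent window once and use it in sections 3.1, 6.1, 6.2.1 and 6.2.8.
- **Subjects already enrolled.** State how those admitted under the current wording are handled.

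The cost is a protocol amendment with IRB/EC documentation before implementation (sections 10.3 and 12.1) at up to 20 sites, plus one small data field. Some subjects may have no documented LVEF in the chosen window. The sample size (140 evaluable, 150 enrolled), the power and the critical values (89 of 140 responders, 15 of 150 subjects with an event) do not change.
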